**Tertiary objectives:**

CCI

 By “medically assessed” it is meant that the infant was evaluated by a healthcare professional (physician, nurse, etc) for the lower respiratory tract illness.

Case definitions for *RSV-associated medically attended RTIs (RSV-MA-RTIs)*, RSV associated LRTIs and surveillance for potential LRTIs are briefly summarized in Section 4.2.6.

An infant is defined as a child younger than 1 year of age; a neonate is defined as an infant 28 days old or less.

Maternal and neonatal AESI and pregnancy outcomes should be recorded in the eCRF along with assessment of level of diagnostic certainty by GAIA definitions when applicable. Of note, some events of interest fall under a single category but have multiple subcategories. For example, hypertensive disorders of pregnancy is an event with three subcategories that include: 1) gestational hypertension; 2) pre-eclampsia; and 3) pre-eclampsia with severe features (including eclampsia). For each event, the investigator should identify the event and select the applicable sub-category.

The following adverse events are listed by GAIA as events of interest, but will not, for purposes of this study, be reported as AESIs. If any of these events meets the definition for an SAE, the event should be reported as such in the eCRF and the SAE narrative should contain enough information to permit assessment of level of diagnostic certainty by GAIA criteria:

Pregnancy-related: antenatal bleeding (morbidly adherent placenta, placental abruption, cesarean scar pregnancy, uterine rupture), postpartum hemorrhage, non-reassuring fetal status, oligohydramnios, polyhydramnios, gestational liver disease (intrahepatic cholestasis of pregnancy, acute fatty liver of pregnancy), maternal sepsis.

Neonatal: neonatal encephalopathy, congenital microcephaly (postnatally or prenatally diagnosed), neonatal infections (blood stream infections, meningitis, respiratory infection), respiratory distress in the neonate, failure to thrive, large for gestational age, macrosomia.

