**Table 21 Reporting pregnancy outcomes with or without congenital anomalies as AESIs and/or SAEs**

Congenital anomalies*	Live birth		Fetal death /stillbirth		Elective / Therapeutic Termination	
	AESI	SAE	AESI	SAE	AESI	SAE
None	-	-	-	X	-	X
Major 	X	if reportable per MACDP 	-	X	-	X
Minor 	-	if reportable per MACDP 	-	X	-	X

\* In the event of infant’s participation in the study, congenital anomalies are to be reported in the infant’s eCRF.

However, when there is no live birth, or no signed informed consent for the infant or the congenital anomaly is being reported for a subsequent pregnancy, it will be encoded in the maternal participant’s eCRF.

Structural or functional defects that require surgical and/or medical treatment and that have serious adverse effects on health or development (functional) or have significant cosmetic impact.

Anatomic variants or defects that do not have serious medical, functional or cosmetic consequences for the child.

Metropolitan Atlanta Congenital Defects Program (MACDP) 6-Digit Code Defect List

Additional guidance when congenital anomalies are present follows:

The term “congenital anomaly” is broad. GSK uses the case definitions provided in the Centers for disease Control and Prevention (CDC) Metropolitan Atlanta Congenital Defects Program guidelines, with specific reference to the MACDP 6-Digit Code Defect List [MACDP, 2021] to ensure that the collection and recording of these data is complete and consistent across studies and projects.

To report a pregnancy outcome of live birth with congenital anomaly as an SAE per these guidelines, an infant must have a birth defect that is *included in MACDP surveillance data* per the MACDP 6-Digit Code Defect List. (Congenital anomalies that are not included in MACDP surveillance data may be reported as medically attended or serious adverse events, if appropriate).

The characterization of major and minor congenital anomalies will follow CDC definitions [CDC, 2019]. Major congenital anomalies are structural or functional defects that require surgical and/or medical treatment and that have serious adverse effects on health or development (functional) or have significant cosmetic impact. They are always reported as AESIs, even if they are not reportable as SAEs.

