**Table 41 Congenital Microcephaly**

Congenital microcephaly, also referred to as primary microcephaly due to its presence in utero or at birth, is a descriptive term for a structural defect in which a fetus or infant’s head (cranium) circumference is smaller than expected when compared to other fetuses or infants of the same gestational age, sex and ethnic background

Levels of Diagnostic Certainty (1 highest level to 4 lowest level of certainty)	
Postnatally Diagnosed Microcephaly	
Level	Description
1	
Live birth, stillbirth, or spontaneous or therapeutic abortion of at least 24 weeks of Gestational Age (GA)~ AND Head Circumference (HC) 2 Standard Deviations (SD) below mean or <3rd percentile according to GA and gender, using appropriate standardized reference charts for the population (e.g., WHO growth reference charts if GA ≥37 weeks and Intergrowth-21st reference charts for GA 24–36 weeks) AND Measured between 24–36 hours after birth or end of pregnancy. ~GA assessed based on certain Last Menstrual Period (LMP) with confirmatory 1st trimester or 2nd trimester ultrasound (US) scan, intrauterine insemination (IUI), or embryo transfer date

2a	
Live birth, stillbirth, or spontaneous or therapeutic abortion of at least 24 weeks of GA~ AND HC 2 SD below mean or <3rd percentile according to GA and gender, using appropriate standardized reference charts for the population (e.g., WHO growth reference charts if GA ≥37 weeks and Intergrowth-21st reference charts for GA 24–36 weeks) AND Measured
 
 
• within the first 24 hours§
 
OR
 
• >36 hours and up to 6 weeks after birth or end of pregnancy with no apparent post-natal insult resulting in microcephaly
 
 
~GA assessed based on certain LMP with confirmatory 1st trimester or 2nd trimester US scan, IUI, or embryo transfer date §Take into account the variability in this period based on molding of the head

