
To evaluate pregnancy outcomes and pregnancy-related adverse events of special interest after a single IM dose of the RSV Maternal vaccine administered to maternal participants, from Visit 1 up to 6 weeks after delivery (Visit 4).
	
Pregnancy outcomes⁵ from Day 1 (Visit 1) up to 6 weeks after delivery (Day 43 post-delivery, Visit 4). These include live birth with no congenital anomalies, live birth with minor congenital anomaly(ies) only; live birth with at least one major congenital anomaly, fetal death/still birth (antepartum or intrapartum) with no congenital anomalies, fetal death/still birth (antepartum or intrapartum) with only minor congenital anomalies, fetal death/still birth (antepartum or intrapartum) with at least 1 major congenital anomaly; elective/therapeutic termination with no congenital anomalies; elective/therapeutic termination with only minor congenital anomalies, and elective/therapeutic termination with at least 1 major congenital anomaly.
 
Pregnancy-related adverse events (AEs) of special interest from Day 1 (Visit 1) up to 6 weeks after delivery (Day 43 post-delivery, Visit 4). These include maternal death, hypertensive disorders of pregnancy (gestational hypertension, pre-eclampsia, pre-eclampsia with severe features including eclampsia), fetal growth restriction, pathways to preterm birth (premature preterm rupture of membranes, preterm labor, provider-initiated preterm birth), gestational diabetes mellitus, chorioamnionitis.^{4,5}

To evaluate the occurrence of neonatal AEs of special interest (reported up to 6 weeks after birth), in infants born to mothers who were vaccinated with a single IM dose of the RSV Maternal vaccine
	
The occurrence of neonatal AEs of special interest (reported up to 6 weeks after birth). These include small for gestational age, low birth weight including very low and extremely low birth weight (<2500 g, <1500g, <1000g), congenital anomalies (major external structural defects, internal structural defects, functional defects), neonatal death (in an extremely preterm birth [22≤GA<28 weeks], in a preterm live birth [28≤GA<37 weeks], or in a term live birth), preterm birth.^{4,5}

Tertiary objectives:

CCI

¹By “medically assessed” it is meant that the infant was evaluated by a healthcare professional (physician, nurse, etc) for the lower respiratory tract illness.

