²Case definitions for *RSV-associated medically attended RTIs*, RSV associated LRTIs, surveillance for potential LRTIs, are briefly summarized in Section 9.2.2.

³An infant is defined as a child younger than 1 year of age; a neonate is defined as an infant 28 days old or less.

[figure not shown]
⁴Maternal and neonatal AESI and pregnancy outcomes should be recorded in the eCRF along with assessment of level of diagnostic certainty by GAIA definitions when applicable. Of note, some events of interest fall under a single category but have multiple subcategories. For example, hypertensive disorder of pregnancy is an event with three subcategories that include: 1) gestational hypertension; 2) pre-eclampsia; and 3) pre-eclampsia with severe features (including eclampsia). For each event, the investigator should identify the event and select the applicable sub-category.

⁵The following adverse events are listed by GAIA as events of interest, but will not, for purposes of this study, be reported as AESIs. If any of these events meets the definition for an SAE, the event should be reported as such in the eCRF and the SAE narrative should contain enough information to permit assessment of level of diagnostic certainty by GAIA criteria:

- Pregnancy-related: antenatal bleeding (morbidity adherent placenta, placental abruption, cesarean scar pregnancy, uterine rupture), postpartum hemorrhage, non-reassuring fetal status, oligohydramnios, polyhydramnios, gestational liver disease (intrahepatic cholestasis of pregnancy, acute fatty liver of pregnancy), maternal sepsis.
- Neonatal: neonatal encephalopathy, congenital microcephaly (postnatally or prenatally diagnosed), neonatal infections (blood stream infections, meningitis, respiratory infection), respiratory distress in the neonate, failure to thrive, large for gestational age, macrosomia.

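### Microcephaly that also qualifies as a major anomaly is excluded from the neonatal AESIs by one rule and required by another, so the AESI anomaly count can depend on which rule a site followed

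*Protocol*

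**What the plan says.** **The exclusion.** Footnote 5 of Protocol Table 4 (Section 3) names GAIA events of interest "but will not, for purposes of this study, be reported as AESIs". The neonatal part of the list begins "Neonatal: neonatal encephalopathy, congenital microcephaly (postnatally or prenatally diagnosed"). It sets no condition on severity. A listed event that meets the SAE definition is still reported as an SAE. SAP Table 1 footnote 5 carries the same entry, "congenital microcephaly (postnatally or prenatally diagnosed").

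**The inclusion.** Protocol Section 8.3.4.2 defines the term: "Major congenital anomalies are structural or functional defects that require surgical and/or medical treatment and that have serious adverse effects on health or development (functional"), with significant cosmetic impact as an alternative. It then says "They are always reported as AESIs, even if they are not reportable as SAEs", and names no exception. Table 21 in that section marks a live birth with a major anomaly as an AESI. Minor anomalies are expressly not AESIs.

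**The link.** Appendix 9, Table 41 says congenital microcephaly "is a descriptive term for a structural defect in which a fetus" or infant has a head smaller than expected.

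**The endpoint.** The neonatal AESI endpoint (SAP Table 1, matching Protocol Table 4) includes "congenital anomalies (major external structural defects, internal structural defects, functional defects"). Protocol 9.4.4.4 and SAP 5.4.1 restate it without the footnote.

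**The concern.** An event definition for a safety endpoint should give the same answer at every site. Here two instructions in force together give opposite answers for one kind of case. A site working from footnote 5 would not flag it as an AESI. A site working from Section 8.3.4.2 would.

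If the analysis counts AESIs as flagged, the congenital-anomaly line mixes the two practices and the reader of the report cannot tell how. This trial was stopped for an infant safety signal, so its neonatal AESI tables will be read closely and should be reproducible from the written rules.

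**Working it through.** The documents attach no rate, sample size or test to this point, so there is no stated figure to reproduce. The check is to take each kind of infant and apply both rules.

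1. **Microcephaly that does not meet the major conditions.** Footnote 5: not an AESI. Section 8.3.4.2: a minor anomaly, not an AESI. The rules agree.
2. **Microcephaly that does meet the major conditions.** Footnote 5: not an AESI. Section 8.3.4.2: always an AESI. The rules conflict.
3. **Another major anomaly, not on the footnote list.** An AESI under both. The rules agree.
4. **Microcephaly together with another major anomaly.** The infant is in an infant-level anomaly count either way. Only a count of individual events changes.

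So the conflict is confined to case 2, and for an infant-level count to case 2 without another major anomaly.

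**Does other text settle it?**

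- Appendix 9 warns that not every event it lists is an AESI. It leaves the microcephaly row unflagged and flags the congenital-anomaly row. It does not say what to do when one case belongs to both rows.
- Section 10.3.5 does not list microcephaly. It does list structural and functional defects, and requires a listed diagnosis to be reported as an AESI once there is enough evidence for it.
- The edge of case 2 is itself blurred. Table 42 describes major anomalies by potential impact, without the treatment condition in Section 8.3.4.2. Section 10.3.5 attaches the word major only to external structural defects.

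**Scale.** The Day 43 interim analysis in Protocol Section 2.3 covers 5235 infants, 3496 of them in the active group, leaving 5235 − 3496 = 1739 controls. One infant classified differently moves a proportion by:

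- overall: 1/5235 = 0.019 percentage points
- active: 1/3496 = 0.029 percentage points
- control: 1/1739 = 0.058 percentage points

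The number of such infants is not in the documents.

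**The case against.** The strongest reply is that the specific rule governs the general one. Footnote 5 names microcephaly, the SAP repeats it, Appendix 9 leaves it unflagged, and Section 10.3.5 omits it. That is the natural reading and may be what was meant, but no text says so, and the word always in Section 8.3.4.2 points the other way. Section 8.3.4.2 also refers sites to the Study Procedures Manual. That manual is not available here, so it cannot be shown that sites had no guidance.

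Three further points stand.

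- Cases need not be lost. Footnote 5 keeps the SAE route, anomalies on the MACDP list are SAEs, and medically attended AEs are tabulated by group.
- Allocation was minimised by center (Section 6.3.3), so differences in site habit should roughly balance between arms, at least while sites were blinded.
- The methods column in SAP 5.4.1 is redacted and the table list is a separate document (SAP 10.2). One can say only that the readable text gives no derivation rule.

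A reader might go further in three ways that the documents do not support.

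- **That every microcephaly is an AESI because it is a structural defect.** Section 8.3.4.2 asks for more than that, and nothing says microcephaly is always major.
- **That the pregnancy-outcome endpoint is contradictory too.** Footnote 5 is marked on that endpoint, but its wording governs AESI reporting only. The categories depend on whether an anomaly is major, minor or absent. Nothing in the footnote turns a birth with microcephaly into one without anomalies.
- **That the size can be had by multiplying the infants by the share beyond the Table 41 head-circumference threshold, and that a relative risk is diluted accordingly.** Footnote 5 counts none of those infants and Section 8.3.4.2 counts only the major cases, so neither rule produces that number.

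**Conclusion.** The point holds in a narrow form. For microcephaly that meets the major conditions of Section 8.3.4.2, the Protocol and SAP give two incompatible instructions, and no readable text ranks them. One endpoint is affected: the congenital-anomaly component of the neonatal AESIs.

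The number of infants involved is unknown. It is probably small, because the case must be major and because women were eligible only if a fetal anomaly scan showed no significant malformation (Section 5.1.1). That judgement rests on those two filters, not on a reported rate. No bias between arms is shown. The defect is a count that cannot be reproduced from the written rules.

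**What to change.** In SAP 5.4.1, derive the congenital-anomaly AESI count by one rule applied to all recorded AESI, SAE and MAE terms, whatever AESI flag the site set. State whether microcephaly meeting the major definition is counted, and which definition of major applies. Give microcephaly its own row by arm, and show the AESI anomaly total with and without it.

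Leave the pregnancy-outcome categories unchanged. Taking microcephaly out of them would remove genuine major anomalies from a safety endpoint that footnote 5 does not govern.

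Reconcile footnote 5 with Section 8.3.4.2 so that the record is consistent. Enrollment has stopped and the 6-month analysis is done, so rewording alone cannot change how sites reported past cases. The derivation rule is the part that repairs the tables.

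The cost is a short SAP clarification and one or two extra table rows, from data already collected.

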## 4. STUDY DESIGN

### 4.1. Overall design

The study is a Phase III, double-blind, randomized, placebo controlled, multi-centric, multi-country study with 2 parallel groups. At least 20% of participants will be enrolled at centers in the U.S.

The study design is adaptive, with recruitment and randomization occurring in 2 sequential stages, A and B. Stage B may begin immediately after the last participant is randomized in Stage A.

To encourage participation in the study and to achieve recruitment targets on time, the study sites will be encouraged to manage recruitment plans using methods that are acceptable within local regulations such as advertisements in news media and/or use of posters and fliers. All such recruitment materials will be approved by the local ethics committees.

Following verification that inclusion/exclusion criteria are met, all maternal participants will be randomized 2:1 to receive either GSK Biologicals’ RSV Maternal (RSVPreF3) vaccine or the placebo control.

Study procedures in Stage A differ from those in Stage B in 2 ways.

[figure not shown]
During Stage A only:

- All maternal participants will be asked to report solicited events during the 7 days post-dose, and
- Maternal and (as yet unborn) infant participants will be further randomized into sub-cohorts for blood sample collection for the assessment of immune response.

Figure 1 and Figure 2 provide overviews of the study design for maternal and infant participants, respectively.

Section 1.3 provides Schedules of Activities (SoAs) for maternal and infant participants. Section 9.5.1 describes the sequence of analyses for maternal and infant participant data.

**Figure 1 Study design overview – maternal participants (Amended 23 February 2023)**

GA = Gestational age; I = immune response; (S)AE = (serious) adverse event; RTI = respiratory tract illness  
Visit 2 may be replaced by Visit 3 in case of premature delivery.

All = all participants

Refer to Section 6.3.2 for detailed description of Stage A and Stage B. Refer to Section 6.3.2.1.1 for additional description of the Stage A sub-cohort.

Solicited events will be evaluated for all participants in **Stage A only**

[figure not shown]
\* Any pregnancy-related event of special interest identified after Visit 4 should also be reported.

In addition to the monthly contacts between Visit-2 and the Delivery visit, additional not pre-specified visits and contacts (any desired frequency) can be made between Visit-2 and the Delivery visit, as per investigator’s or maternal participant’s discretion.

As from protocol Amendment 4, blood samples will be collected at delivery from all maternal participants. Placental samples will be collected at delivery from all maternal participants, if feasible.

**Due to the stop on study enrollment and vaccination, nasal swab samples will no longer be collected from any maternal participant and no MA-RTI assessment visit will be performed, but the MAEs associated with an RTI will continue to be reported, as applicable.**

**Figure 2 Study design overview – infant participants**

I = immune response; (S)AE = (serious) adverse event; RTI = respiratory tract illness

Stage A + Stage B – all participants:

\*If cord-blood was not collected at delivery/birth, a blood sample should be collected from the infant **within 72 hours post birth**. Applies to all participants in Stage A and Stage B.

\*\*Any Neonatal AE of specific interest identified *after* Day 43 should also be reported.

An additional recommended safety contact may be performed 8-days post-birth if deemed necessary by the investigator or by the parent/LAR(s).

NOTE: Due to the stop on study enrollment and vaccination, blood samples will no longer be collected at V2-NB, V3-NB or V4-NB.

- Study Type: self-contained
- Study Duration: Approximately 10 to 11 months (including the screening visit) for maternal participants; approximately 1 year after birth for infant participants.
- Blinding is as described in [Table 5](#) and [Table 6](#).
- Randomized intervention allocation is described in [Table 5](#), [Table 6](#), and Section 6.3.
- Study (intervention) groups are described in [Table 5](#) and [Table 6](#).
- Data collection: standardized Electronic Case Report Form (eCRF) e-Diaries will be used to collect solicited event data (Stage A mothers only). Unsolicited Adverse event data will be collected through questioning at study visits/contacts and reported into the eCRF, as appropriate. Parent(s) / LAR(s) will use a Paper Diary to record RTI symptoms experienced by infant participants; these data will be transcribed into the eCRF as appropriate.
- Safety monitoring will be conducted by an unblinded Independent Data Monitoring Committee (IDMC) and by an unblinded Safety Review Team\* (Section 8.2.3).

\* *Due to the safety signal observed, the study was fully unblinded to ensure the safety of the participants.*

**Table 5 Study groups, sub-cohorts, interventions, and blinding foreseen in the study: Stage A**

Approximately 4600 maternal participants will be randomized during Stage A.

Study groups	Maternal participants (M)				Infant participants (I)			Study Groups for Randomization  (Allocation 12:2:2:2:6:1:1:1)	Blinding		
	~Number	Age in Years (Min/Max)	Intervention name	Maternal Blood Sampling Sub-cohorts		Infant Blood Sampling sub-cohorts			M only	M + I	I only
				Name	~Number	Name	~Number		Screen-ing	Up to D181 post delivery/ birth	D271, D366 post delivery/ birth
									-	Double blind	Double blind
RSV_MAT	~3067	18-49	RSV_MAT	RSV_MAT_0	~2040	RSV_MAT_0	~2040	RSVMAT_0	•	•	•
		18-49	RSV_MAT	RSV_MAT_I	~1020	RSV_MAT_BS1	~340	RSVMAT_BS1		•	
						RSV_MAT_BS2	~340	RSVMAT_BS2		•	
						RSV_MAT_BS3	~340	RSVMAT_BS3		•	
Control	~1533	18-49	Control	Control_0	~1020	Control_0	~1020	Control_0	•	•	•
		18-49	Control	Control_I	~510	Control_BS1	~170	Control_BS1		•	
						Control_BS2	~170	Control_BS2		•	
						Control_BS3	~170	Control_BS3		•	

Control = Placebo; Infant sub-cohorts are abbreviated “BS1;” “BS2;” BS3” and correspond to visits 2-NB (Day 43), 3-NB (Day 121) and 4-NB (Day 181), respectively.

RSVMAT\_0 and Control\_0 = maternal and infant participants who are not in a sub-cohort for immune response assessment.

RSVMAT\_I and Control\_I = maternal sub-cohorts for immune response assessment.

RSVMAT\_BS1, \_BS2, \_BS3 = infants born to women in the RSVMAT\_I sub-cohort and evaluated for immune response at the designated timepoint (D43, D121 or D181).

Control\_BS1, \_BS2, \_BS3 = infants born to women in the Control\_I sub-cohort evaluated for immune response at the designated timepoint (D43, D121 or D181).

